9.2.2. Sample Size Sensitivity

The within-subject SD of 140 ml for trough FEV₁ used for the sample size calculations was based on two previous cross-over responder studies in COPD subjects evaluating trough FEV₁ at Week 2. If the standard deviation observed in this study is different from the estimated value used in the sample size calculation, the power to determine non-inferiority based on trough FEV₁ at Week 8 will be affected. Table 4 illustrates the power which would be obtained with various standard deviations, assuming the number of evaluable subjects remains constant at 168 and the non-inferiority margin is -50 mL.

Within-subject SD (mL)	Power for Margin of -50 mL
100	>99%
120	97%
140	90%
160	81%
180	72%

Table 4Impact on Power of Different Estimates of Standard Deviation for
Trough FEV1

If the within subject SD increased to 180 mL, the study would have 72% power to conclude non-inferiority based on a margin of -50 mL. If the SD were 100 mL then the study would have >99% power to conclude non-inferiority.

Based on a within subject SD of 140 mL and a sample size of 168 evaluable PP subjects, the lower confidence bound for the treatment difference would be greater than 0 at an observed treatment difference of 30 mL [detectable effect].

Based on a within subject SD of 140 mL and a sample size of 186 ITT subjects, the study would conclude superiority (i.e. lower confidence bound > 0) with a treatment difference of 29mL [detectable effect].

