7. PRIMARY STATISTICAL ANALYSES

7.1. Efficacy Analyses

7.1.1. Overview of Planned Efficacy Analyses

The primary efficacy analyses for the primary endpoint will be on the PP population. All outputs produced for the primary endpoint will be repeated on the ITT population. Further investigation will be done if the results from the PP analysis are not consistent with the results from the ITT analysis for the primary endpoint. In addition, a tipping point analysis will be carried out as a sensitivity analysis for the primary endpoint of trough FEV₁ at Week 8 on the PP and ITT population in order to assess the impact of missing data on conclusions of non-inferiority and superiority.

Table 4 provides an overview of the planned efficacy analyses for the primary endpoint, with full details of data displays being presented in Appendix 13: List of Data Displays.

Table 4 Overview of Planned Efficacy Analyses for the Primary Endpoint

Endpoint	Change from Baseline [1]						
	Stats Analysis Summary Ind			Indiv	ridual		
	Т	F	L	Т	F	F	L
Trough FEV ₁							
Trough FEV ₁ at Week	Y	Y3		Y	Y2		Y
8 (ITT and PP							
population)							
Tipping point on	Y						
Trough FEV ₁ at Week							
8 (ITT and PP							
population)							

NOTES :

- T = Table, F = Figure, L = Listing, Y = Yes display generated.
- Stats Analysis = Represents TFL related to any formal statistical analyses (i.e. modelling) conducted.
- Summary = Represents TFL related to any summaries (i.e. descriptive statistics) of the observed raw data.
- Individual = Represents FL related to any displays of individual subject observed raw data.
- [1] Analysis and Summaries to include absolute values too.
- ² Box plot and empirical distribution function plot for change from baseline.
- ³ Figures include all time points produced for change from baseline only.

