7.1.2. Planned Efficacy Statistical Analyses

Primary Statistical Analyses					
Endpoint(s)					
 Trough FEV₁ at Week 8 (results for trough FEV₁ at Week 4 will be obtained from the same analysis) 					
Model Specification					
 Trough FEV₁ at Week 8 will be analysed for the PP population using a mixed model repeated measures (MMRM) including data recorded at each of Week 4 and Week 8. The following covariates will be included in the model: period baseline (the difference between a subject's baseline in each treatment period and the mean overall baseline for that subject), mean baseline (the mean of the baselines in each of the two treatment periods), period, treatment, visit, visit by period baseline, visit by mean baseline and visit by treatment interactions, where visit is nominal Subject will be fitted as a random effect. Two models will be fitted; one with a response variable of trough FEV₁, and one with a response variable of change from baseline in trough FEV₁. An unstructured covariance structure for the R matrix will be used by specifying 'type=UN' on 					
the REPEATED line.					
• The Kenward and Roger method for approximating the denominator degrees of freedom and correcting for bias in the estimated variance-covariance of the fixed effects will be used. If this method does not run, the residual method will be used instead.					
Example SAS code					
proc mixed data=start; class subject period treatment visit; model endpoint=period treatment visit mean_base period_base visit*period_base visit*mean_base visit*treatment / ddfm=kr; random intercept / subject=subject; repeated visit / subject=subject*period type=un; Ismeans visit*treatment / cl diff e; ods output Ismeans=Ismeans; ods output diffs=diffs; run;					
Model Checking & Diagnostics					
Refer to Appendix 11: Model Checking and Diagnostics for Statistical Analyses.					
Model Results Presentation					
 Least squares (LS) mean and LS mean changes from baseline with their corresponding standard errors (SEs) will be presented for each treatment by visit, together with estimated treatment differences (UMEC/VI 62.5/25 vs. TIO/OLO 5/5), corresponding 95% CIs and p-values. A plot of LS mean changes from baseline and 95% CIs for each treatment by visit will be generated 					
 The type III tests of fixed effects and the covariance parameter estimates from the model will be presented in two tables. 					

Summary Results Presentation

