• Summary of baseline FEV₁ will be presented by treatment for all subjects.

Primary Statistical Analyses

- A box plot and an empirical distribution function plot of change from baseline in trough FEV₁ at Week 8 will be produced.
- Summary statistics for raw and change from baseline in trough FEV₁ at each visit and for each treatment will be presented on the same table.

Sensitivity and Supportive Statistical Analyses

- The analysis and results presentation will be repeated for the ITT population (with the exception of the box plot and empirical distribution function plot).
- Sensitivity of the results to missing data will be assessed using Tipping Point Analysis for both the PP and ITT population. Analysis of the primary endpoint at Week 8 will be run with missing data imputed under a variety of assumptions for the mean of the missing data. This will be done for both study arms separately. These analyses will allow for determination of the 'tipping point(s)' which is, the mean values for missing data that would cause a change in the conclusion of a)non-inferiority and b)superiority as assessed by the lower limit of the two-sided 95% CI. Multiple- imputation will be used for imputing the Week 8 endpoint of interest for subjects who had missing on-treatment data at Week 8.

For each imputation, a random draw will be made from a normal distribution with mean equal to the corresponding assumed mean change from baseline and standard deviation taken from the observed change from baseline data for the combined treatment arms at the Week 8 visit. Data for subjects with missing baseline values will not be imputed. Analysis of the complete Week 8 dataset will be carried out using an ANCOVA model with covariates of treatment group and baseline for that particular period (Note: not the period baseline).

Initially the same mean change from baseline will be assumed for subjects who withdrew from both treatment arms. The assumed values for the mean change from baseline at Week 8 will vary from -150mL to +150mL in increments of 50mL.

The analysis will be repeated assuming different mean changes from baseline for subjects who withdrew from each treatment arm. For each value of the assumed mean change from baseline for subjects who withdrew from UMEC/VI, the full range of values for subjects who withdrew from TIO/OLO will be investigated.

Seeds for multiple imputation analyses will be set using the following SAS code:

```
data seed1;

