   number=round(10000*ranuni(0),1);
   output;
run;
```

proc print; run;

The seeds generated and assigned to each analysis will be documented separately prior to DBF. A table will be produced displaying the two-sided 95% lower confidence limit of the Week

Sensitivity and Supportive Statistical Analyses

8 treatment differences under the above assumptions for the mean changes from baseline for each of the treatment arms

• An assessment of whether the effect of treatment is modified by the interaction of

Period

Period baseline

Mean baseline

will be made. Interactions with treatment will be investigated by fitting separate MMRM models with the same terms as the main model, and adding in treatment by factor by visit interaction. Contrast statements will be used to obtain the p-value for the treatment by factor interaction at Week 8. The interaction term will be tested at the 10% significance level. If that p-value is >=0.10 the interaction will be considered not significant. If the p-value is <0.10, further investigation will be performed, for example running analysis by each level of the factor, or for subgroups above and below the median. This will be assessed for the PP population.

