8.1.2. Planned Efficacy Statistical Analyses for Other Efficacy Endpoints

8.1.2.1. Responder FEV₁

Statistical Analyses for Proportion of Trough FEV₁ Responders Endpoints

• Proportion of responders according to FEV₁ (a responder is defined as a ≥100mL change in Trough FEV₁ from baseline)

Model Specification

- At each visit, the proportion of subjects achieving a ≥100mL change in Trough FEV₁ from baseline will be analysed using a generalised linear mixed model.
- The following covariates will be included in the model: period baseline, mean baseline, period, treatment, visit, visit by period baseline, visit by mean baseline and visit by treatment interactions, where visit is nominal.

Example SAS code

proc glimmix data=start; class subject period treatment visit; model endpoint(descending)=period treatment visit mean_base period_base visit*period_base visit*mean_base visit*treatment / dist=binary link=logit ddfm=kr solution; random intercept / subject=subject; random visit / subject=subject*period residual type=un; lsmeans visit*treatment / diff;

ods output Ismeans=Ismeans;

ods output diffs=diffs;

run;

Statistical Analyses for Proportion of Trough FEV₁ Responders

• Note: The residual statement turns the random statement into a repeated statement

Model Checking & Diagnostics

• Refer to Appendix 11: Model Checking and Diagnostics for Statistical Analyses.

Model Results Presentation

The odds ratio, 95% CI and p-value of UMEC/VI 62.5/25 vs. TIO/OLO 5/5 will be presented.

Summary Results Presentation

• The number and percentage of responders and non-responders at each visit will be summarized on the same table as the analysis results detailed above.

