E-RS	X	 Provided at least 4 days are non-missing, the baseline is calculated as the average of measurements over the duration stated below: Period 1: Values recorded between the latest of (7 days prior to Visit 2 and the day of Visit 1) and the Day before Visit 2 Period 2: Values recorded between the latest of (7 days prior to Visit 5 and the day of Visit 4) and the Day before Visit 5.

For FEV₁ and FVC, IC, rescue use, CAT and E-RS analyses:

- Mean (subject level) baseline is defined as the mean of the baselines in each period for each subject.
- Period baseline is defined as the difference between the baseline and mean baseline for each period and each subject.

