10.5.2.2. Derivations and Handling of Missing Baseline Data

Definition	Reporting Details
Change from Baseline	= Post-Dose Visit Value – Baseline
Percentage Change from Baseline	= ((Post-Dose Visit Value – Baseline)/Baseline)*100
NOTES :	

 Unless otherwise specified, the baseline definitions specified in Section 10.5.2.1 Baseline Definitions will be used for derivations for endpoints / parameters and indicated on summaries and listings.

• Unless otherwise stated, if baseline data is missing no derivation will be performed and will be set to missing.

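### As written, the tipping-point ANCOVA ignores the crossover pairing, so with positive residual correlation its lower limit is too low before anything is imputed

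*SAP*

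**What the plan says.** SAP 7.1.1 plans a tipping-point analysis of the primary endpoint on both the PP and ITT populations, "in order to assess the impact of missing data on conclusions of non-inferiority and superiority". SAP 7.1.2 (Sensitivity and Supportive Statistical Analyses) imputes missing Week 8 values from a normal distribution with an assumed mean change, and analyses the completed data "using an ANCOVA model with covariates of treatment group and baseline for that particular period". A note adds that this covariate is not the derived period baseline. No model code is given, only code for seeds, and Appendix 10.7.2.3 simply refers back to 7.1.2.

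The assumed means run from -150 to +150 mL in steps of 50, first equal in the two arms and then crossed. For the output, "A table will be produced displaying the two-sided 95% lower confidence limit of the Week" 8 differences. No row without imputation is described.

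The primary model in the same section contains period, mean baseline and period baseline, and states: "Subject will be fitted as a random effect". Protocol 4.4 justifies the crossover by the reduced variability of within-subject comparison, and Protocol 9.2.1 sizes the trial on a within-subject SD of 140 mL.

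**The concern.** The tipping points are read from the lower 95% limit, so its width matters as much as the estimate. An ANCOVA on treatment and own-period baseline, with no subject term, leaves any between-subject variation that baseline does not explain in the error term. The interval then widens for a reason unrelated to missing data.

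If the primary lower limit lies fairly close to -50 or 0 mL, some grid cells could fall below that threshold only because the model changed. The table would present this as fragility to missing data, and without an unimputed row from the same model a reader could not separate the two causes.

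**Working it through.** **Inputs.** From Protocol 9.2.1: within-subject SD 140 mL, 168 evaluable subjects, margin -50 mL, true difference 0, one-sided 2.5%, 220 randomised, 15% withdrawal (33 subjects). Assumed, because the documents do not give them: rho from 0 to 0.7; in simulations also a between-subject baseline SD of 400 mL and baseline noise of 0, 60 or 99 mL.

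**1. Reproduce the plan.** Paired SE = 140 × √(2/168) = 15.28 mL; half-width 1.96 × 15.28 = 29.9 mL. This matches Protocol 9.2.2, where "the lower confidence bound for the treatment difference would be greater than 0 at an observed treatment difference of 30 mL". Power = Φ(50/15.28 − 1.96) = Φ(1.31) = 90.5%, against 90% stated. The planned precision is therefore that of a paired analysis.

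**2. Drop the subject term, complete pairs, noiseless baselines.** The error variance becomes 140²/(1 − rho), so SE = 15.28/√(1 − rho). The implied residual between-subject SD is 140 × √(rho/(1 − rho)). Drops are from unrounded values.

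| rho | Implied SD (mL) | SE (mL) | Half-width (mL) | Drop in lower limit (mL) | Lower limit at observed 30 mL |
|---|---|---|---|---|---|
| 0 | 0 | 15.3 | 29.9 | 0 | 0.1 |
| 0.1 | 47 | 16.1 | 31.6 | 1.6 | -1.6 |
| 0.3 | 92 | 18.3 | 35.8 | 5.8 | -5.8 |
| 0.5 | 140 | 21.6 | 42.3 | 12.4 | -12.3 |
| 0.7 | 214 | 27.9 | 54.7 | 24.7 | -24.7 |

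A simulation gave SEs of 16.1 / 18.3 / 21.4 / 27.7 mL at rho 0.1 to 0.7, against about 15.3 mL paired.

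At rho 0.5 the estimate itself still has SD 15.28 mL. The chance that the limit clears -50 mL at a true difference of 0 is therefore Φ((50 − 42.3)/15.28) = Φ(0.50) = 69%, against 90.5%, and the interval covers 99.4%. At an observed difference of 0 the limit reaches -50 mL when rho = 1 − (29.9/50)² = 0.64.

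**3. With imputation.** Simulation: 220 randomised, 33 withdrawals (assumed 16 in period 1 and 17 in period 2), imputed mean change 0 in both arms, 10 imputations with Rubin's rules, 60 trials per cell. The ANCOVA lower limit lay below that of the same model with period and random subject added by:

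| Baseline noise | rho 0.1 | 0.3 | 0.5 | 0.7 |
|---|---|---|---|---|
| 0 mL | 1.3 | 4.7 | 10.1 | 19.0 |
| 60 mL | 1.2 | 4.3 | 9.4 | 18.4 |
| 99 mL | 1.5 | 4.2 | 9.2 | 18.3 |

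To scale this: 220 + 204 = 424 Week 8 values, or 212 per arm, of which about 16.5 are imputed if withdrawals split evenly. One 50 mL grid step in one arm moves that arm's mean by about 50 × 16.5/212 = 3.9 mL. At rho 0.5 the change of model is thus worth more than two grid steps.

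**4. The other two differences from the primary model.** Period: in one simulated scenario a 50 mL period effect moved the ANCOVA SE only from 23.6 to 23.8 mL, and balanced sequences prevent bias. Baseline, at rho 0: if a 99 mL period-to-period shift carries into Week 8, the single own-period baseline costs nothing (SE 15.2 against 15.3 mL). If the 99 mL is noise unrelated to Week 8, it does cost precision (18.5 against 15.3 mL).

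**5. Why the primary baseline terms are not a simple substitute.** SAP 10.5.2.1 says a subject's mean "baseline is defined as the mean of the baselines in each period for each subject", and 10.5.2.2 adds that, unless otherwise stated, "if baseline data is missing no derivation will be performed and will be set to missing". A subject who withdraws before Visit 5 then has neither mean nor period baseline. Under the assumed split, 16 of the 33 imputed values (48%) would be lost.

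**The case against.** The strongest reply is that this is a gap in wording. The covariate lists for FEV₁ responders (SAP 8.1.2.1), rescue use (8.1.2.3) and CAT responders (8.1.2.4) also omit subject, yet their code contains "random intercept / subject=subject". A subject term may well be intended here too. That stands as to intent. But those sections name a mixed model or MMRM and supply code, whereas this one says ANCOVA and supplies none, so two competent programmers could produce different tables.

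It is also fair that all grid cells share one model, so differences between cells do reflect the assumed means. What does not follow is that the cell where the limit crosses a threshold reflects those means alone.

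The size is not set by the documents. Rho 0.7 needs a 214 mL between-subject SD left after baseline adjustment, which nothing in either document supports. At rho 0 with noiseless baselines, the ANCOVA limit was the lower one in only 41-47% of simulated trials. The point is therefore conditional on positive rho.

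A reader might go further and call the own-period baseline an error. The documents do not support that: the SAP's note makes it a deliberate choice, its cost depends on the nature of the baseline variation, and it retains early withdrawals. For the same reason, comparison with the primary-type model, which gives gaps up to 28.8 mL, overstates what can be repaired.

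**Conclusion.** Wrong as written; minor severity. Unless a subject term is added, the table's lower limits ignore the pairing. With rho between 0.1 and 0.7 they are too low by about 1.6 to 24.7 mL in complete data, and by about 1 to 19 mL with imputation relative to a model that fits subject and period. The within-subject SD of 140 mL is the protocol's; rho, baseline noise and the withdrawal split are assumptions.

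For positive rho the error is conservative: it understates robustness. If rho were negative, which is possible when the second baseline tracks the first period's Week 8 value, the model SE would instead be too small.

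A reader might infer that the primary result or the sample size is in doubt, or that a false non-inferiority claim becomes easier. The documents do not support this. The primary model fits subject and period, the sample size reproduces as a paired calculation, and the non-inferiority and superiority claims rest on the primary analysis. The defect touches one sensitivity table, and matters only when the limit is near -50 or 0 mL.

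**What to change.** In SAP 7.1.2, write out the Week 8 tipping-point model with code: treatment, period, own-period baseline and a random subject effect. Keep own-period baseline unless a rule is added that retains subjects with only one period baseline.

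Report the same model without imputation as a reference row, for PP and ITT, so that any change from that row is due to the imputed values. The row will also show any remaining difference from the primary analysis.

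The cost is SAP wording and modest reprogramming before database freeze; no new data are needed.

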4.4. Design Justification

A randomized, cross-over study is a standard, well-established design to evaluate the efficacy and safety of two active drugs and each patient receives both medicines and acts as their own control. A complete block design will allow for within-subject treatment comparisons which will reduce variability in the response as each subject acts as their own control.

The 3-week washout between the two treatment periods is considered sufficient to enable washout of the effects of UMEC/VI and OLO/TIO on lung function measures. In two exercise studies previously conducted by GSK (DB2114417 and DB2114418), there was no evidence of a treatment by period interaction which suggests no evidence of carry over.

The open label design is appropriate as placebo Respimat from Boehringer Inglehiem (BI) is not available to allow a double-dummy design and the Ellipta and Respimat inhalers differ in appearance. The open-label design will have a negligible effect on the

CONFIDENTIAL

spirometric data. Pulmonary function testing is an objective physiologic assessment that provides consistent, reproducible results provided adequate measures are used to ensure standardization of testing procedures. Well-qualified research sites with expertise in pulmonary function testing will be used, and a centralized spirometry vendor will provide standardized equipment and site training and provide quality assessment of each spirometry test based on accepted international lung function testing guidelines. Additionally, individuals performing the testing procedures will be blinded to the administered treatment

While the FDA and EMA guidance for trials assessing bronchodilators in patients with COPD recommend 12 weeks of treatment, the wealth of data with Anoro Ellipta and Stiolto Respimat support that treatment duration of 8 weeks is considered adequate for assessing FEV₁ changes in response to the long-acting bronchodilators under study. Treatment response was shown to reach steady-state after 4 weeks in previous large scale parallel-group studies conducted over 6 months [Donohue, 2013; Decramer, 2014; Maleki-Yazdi, 2014] and after 6 weeks in two 12-week cross over studies [Maltais, 2014]. Similar steady state findings were obtained in the primary efficacy studies conducted over 6 months for Stiolto Respimat [Buhl, 2015].

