10.9. Appendix 9: Examination of Covariates, Subgroups & Other Strata

10.9.1. Handling of Covariates

- Consistency of treatment effect across covariates fitted in the primary efficacy endpoint analysis models will be examined by fitting separate models to examine treatment by period baseline, treatment by mean baseline and treatment by period interactions.
- No formal statistical analysis of sub-groups of the study population will be performed.
- The interaction terms will be tested at the 10% significance level. Significant interactions (<0.10) will be investigated further, for example running the analysis by each category. Continuous covariates may be grouped into dichotomous categories (values above and below median).

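### A median split on period baseline, the SAP's example follow-up to a significant interaction, separates nearly every subject's two periods and gives up the within-subject comparison

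*SAP*

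**What the plan says.** SAP 7.1.2 (Sensitivity and Supportive Statistical Analyses) plans separate interaction models for three factors: period, period baseline and mean baseline. "The interaction term will be tested at the 10% significance level" When p is below 0.10, "further investigation will be performed, for example running analysis by each level of the factor, or for subgroups above and below the median". SAP 10.9.1 repeats the plan and adds: "Continuous covariates may be grouped into dichotomous categories (values above and below median".

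The two baseline covariates are defined in SAP 7.1.2 and 10.5.2.1. Mean baseline is the average of the subject's two period baselines, so it is one value per subject. "Period baseline is defined as the difference between the baseline and mean baseline for each period and each subject", so it takes two values per subject.

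The example code in SAP 7.1.2 fits a random intercept for subject together with "repeated visit / subject=subject*period type=un". Protocol 4.4 justifies the design as follows: "A complete block design will allow for within-subject treatment comparisons which will reduce variability in the response".

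**The concern.** Of the two follow-ups that the SAP names, analysis by level suits period, which has two levels. Period baseline is continuous, so only the median split can apply to it, and neither section makes an exception. A split on mean baseline keeps both of a subject's periods in the same half. A split on period baseline appears to do the reverse by construction.

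At stake is how well an exploratory signal on the primary endpoint can be explained. If the period-baseline interaction reached p<0.10, the example analysis would show two unpaired comparisons, each much less precise than the crossover. The same people would supply the UMEC/VI arm of one half and the TIO/OLO arm of the other.

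**Working it through.** **Inputs from the documents.** 168 evaluable subjects, within-subject SD 140 mL, margin -50 mL, true difference 0 (Protocol 9.2.1); equal allocation to two sequences (Protocol 6.3); covariate definitions (SAP 7.1.2, 10.5.2.1).

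**Assumptions, because the documents give no values.** Between-subject SD of FEV1 400 mL; between-subject SD of response 0 to 150 mL; each baseline carries the same 140 mL within-subject SD.

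**1. The plan's own figures.** SE = 140 × sqrt(2/168) = 15.3 mL, and 1.96 × 15.3 = 30 mL. This matches the 30 mL detectable effect in Protocol 9.2.2. Power against -50 mL is 90.2% (noncentral t, 166 df), matching the stated 90%.

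**2. The two values of period baseline.** With baselines b1 and b2 the mean is (b1+b2)/2. The period baselines are therefore (b1-b2)/2 and -(b1-b2)/2, that is, +d and -d. Pooled over complete subjects the values are symmetric about 0, so the median is 0 even if baseline shifts between periods. In simulation with complete data, 0% of subjects had both periods in one half. With 5 to 15% of records lost per period, on average 1 to 3% of two-period subjects stayed together (maximum 10%). With baselines rounded to 5 mL, about 1% were ties.

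**3. Where the information lies.** Let d be the period baseline in the UMEC/VI period, s the subject effect, tau the drug effect, and bU and bT the slopes on period baseline under each drug. Leaving out period terms:

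- YU - YT = tau + (bU + bT) × d
- YU + YT = constant + (bU - bT) × d + 2s

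The drug effect at d = 0 comes from within-subject differences, in which s cancels. The interaction slope bU - bT comes only from between-subject sums.

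**4. Precision in one half.** A period-baseline half has 168 records from 168 different subjects, about 84 per drug. SE = sqrt(140² + SDb²) × sqrt(2/84), where SDb is the between-subject SD left after adjustment for mean baseline.

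| SDb (mL) | SE (mL) | 1.96 × SE (mL) |
|---|---|---|
| 0 | 21.6 | 42.3 |
| 100 | 26.5 | 52.0 |
| 150 | 31.7 | 62.1 |
| 200 | 37.7 | 73.8 |

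Mean baseline is measured with error variance 140²/2 = 9,800. Under the assumptions it leaves a variance of 400² × 9,800/(400² + 9,800) = 9,234, an SD of 96 mL. With response SD 0, SDb is 96, SE is 26.2 and the half-width is 51 mL. With response SD 150, SDb is sqrt(9,234 + 22,500) = 178, SE is 35.0 and the half-width is 69 mL. Simulation with fitted covariates and t quantiles gives about 51 to 70 mL.

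For comparison, a mean-baseline half holds 84 complete pairs: SE = 140 × sqrt(2/84) = 21.6 mL, half-width about 43 mL with a t quantile, whatever SDb is. The interaction model read at period baseline 0 gives about 30 mL.

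**5. Covariance model.** With one period per subject, subject and subject-by-period are the same unit. Two visits give two variances and one covariance, three moments in all. The code asks for four parameters: one intercept variance and three in the unstructured matrix. The intercept is redundant. If it is dropped, the unstructured matrix is saturated and the treatment effect is estimable.

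**6. Are opposite signs in the two halves caused by the split?** With no drug difference and no interaction, the 10% test fires in about 10% of simulated trials. Among those, drug differences of opposite sign appear in 90 to 96% with the period-baseline split. They also appear in about 81 to 87% with a mean-baseline split after its own trigger. Effects read from the interaction slope at plus and minus the median of |d| differ in sign in about 93% or more. Most of the reversal is therefore selection on a significant interaction around a zero effect.

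**The case against.** The split is not prescribed. The SAP offers it as an example in 7.1.2 and as a possibility in 10.9.1, and the statistician is free to use the interaction model instead. SAP 10.9.1 also rules out formal subgroup analysis, and Appendix 13 lists only a table of interaction significance levels, with no period-baseline subgroup output. Non-inferiority and superiority rest on the confidence interval for the overall comparison. All of this stands, and it makes the point minor.

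The covariance problem is also easily solved by removing one line of code, and the SAP does not say that a subgroup run must reuse the code unchanged. This stands too.

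A reader might go further and infer that the split manufactures a reversal of the drug effect and so threatens the primary result. The material does not support that. A mean-baseline split and the model slope show reversals at similar rates once an interaction has been selected as significant. The between-subject contrast in each half is imprecise but not evidently biased. Nor would the fix stop a chance interaction from appearing, because the slope it reports is itself a between-subject quantity.

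What survives is narrower. For this one factor, the only applicable example gives up the pairing that justifies the design, although a planned model gives a better summary.

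**Conclusion.** The point holds as a minor improvement. The separation of pairs follows from the SAP's definitions alone and needs no outside figure. It is complete for complete data, apart from subjects with equal baselines, and nearly complete when some records are missing.

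The size of the loss depends on assumed SDs. The half-width of 51 to 70 mL per half compares with about 43 mL for a mean-baseline half and 30 mL for the full crossover. If mean baseline removed all between-subject variation (SDb = 0), a period-baseline half would be about as precise as a mean-baseline half, so the excess width comes from the variation that remains. These figures treat Week 8 alone with a linear model in place of the two-visit MMRM.

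Opposite effects in the two halves should not be presented as harm caused by the split alone. The primary MMRM, the interaction test, the sample size and the non-inferiority decision are untouched.

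**What to change.** In SAP 7.1.2 and 10.9.1, limit the median split to mean baseline. For period baseline, replace it with two results from the interaction MMRM already planned: the Week 8 treatment difference with 95% CI at period baseline 0, and the treatment-by-period-baseline slope at Week 8 with 95% CI. State beside them that in this two-period design the slope is estimated between subjects.

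The cost is one or two sentences and an ESTIMATE statement in a model that will be fitted anyway. It needs no new data or subjects. The gain is a summary that keeps the within-subject contrast and its precision of about 30 mL; it does not reduce the chance of a false-positive interaction.
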